We have access to a large (N>70) and unique population of individuals with SCI who have been enrolled in FESRT for at least 6 months. Roughly half have high level SCI between C4 and T4.

II. SPECIFIC AIMS

Aim 1: To determine the magnitude of improvement in aerobic capacity after 3 months of FESRT+NIV compared to FESRT+shamNIV in high level spinal cord injury.

Aim 2: To examine the relationship among gains in ventilation and increases in the determinants of aerobic capacity - maximal cardiac output and arterio-venous oxygen difference after 3 months of FESRT+NIV in high level spinal cord injury.

Aim 3: To examine the acute effect of NIV on FES-row VO₂max in subjects with both high and low level SCI.

III. SUBJECT SELECTION

FES-Row-Training Group

Thirty individuals with high level SCI who have FES-row trained for at least 6 months will be randomized to (continued) FESRT for 3 months with either NIV or sham NIV. Patients will be medically stable and inclusion criteria are SCI at neurological level \geq T4 with American Spinal Injury Association grade A or B or C, aged \geq 18 years of age. Before and after training, we will assess maximal aerobic capacity, ventilation, cardiac output, and arterio-venous oxygen difference. Based on our current data, we hypothesize that only those randomized to NIV will experience further increases in aerobic capacity and that these increases will relate to increased cardiac output and arterio-venous oxygen difference. This project will determine the feasibility and effectiveness of this approach to exercise and will lay the groundwork for a larger study of the impact of FESRT+NIV to improve health and function in those with high level SCI.

FES-Row-Exercise Testing Only Group (Cross-Sectional)

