FES-Row Training. The FES row system will optimize the contribution of the pre-trained muscle components of quadriceps and hamstrings. To maintain the proper training stimulus at the same relative intensity, a maximum FES-rowing test will be performed at baseline for intensity to be determined. The goal is for each volunteer to achieve an exercise intensity of 75-85% maintained for at least 30 minutes performed three times each week. Measurements of force produced at the foot and handle during FES-row training sessions will also be used to monitor training and possibly improve rowing technique. Subjects exercise programs will be tailored specifically to their fitness level but should progress quickly to the prescribed intensity as all subjects

There is no limit or specific requirement for training sessions that must be attended to continue participating in this protocol. Subjects will be encouraged by study staff to attend three training sessions per week. Un-reported missed training session will be followed up with a phone call to document why the training session was missed and to encourage prompt return to training sessions as soon as possible.

Strength Training during FES-RT

As subjects will already have been participating in FES-row training they will also be given the opportunity to continue or start the FES-leg strength training at home concurrently on non FES-rowing days (~3 days/week, 30-60 minutes/session). This will be possible after the subjects have demonstrated the knowledge and ability of proper use of the stimulation unit for home use. This will be

closely monitored, as they will also be FES-rowing three times per week at Spaulding Cambridge.

Study Assessments

FES-Row Training Group

All Assessments will be performed at baseline and after three months of FES-row training. There will be 2 separate FES-VO₂max row tests, 2 separate Cardiac Output row tests and 1 Pulmonary Function test done at each time point (done at least 48-hours apart). Both NIV Support and Sham-NIV groups will perform tests with and without use of the NIV-machine.

FES-Row Exercise Testing Only Group

Subjects will perform FES-VO₂max row tests on separate days with and without the use of NIV to determine maximal aerobic capacity and ventilation. Both FES-VO₂max Row tests will be performed at least 48-hours apart

Measurements and Testing Protocols:

FES-Row-VO₂max Testing

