Individuals will refrain from eating for 2 hours prior, from caffeine and alcohol for 24 hours prior, and from vigorous physical activity for 48 hours prior to testing. Aerobic power will be determined from online computer-assisted open circuit spirometry and expired gas analysis will be performed continuously throughout the test with the Innocor rebreathing system (Innovision, Odense, Denmark, see details below). A heart rate monitor (Suunto, [name]) will be used throughout the tests. The baseline graded FES row test protocol will be based on each individual's initial FES row response, and 1- to 2-minute workloads will be selected to achieve test protocols of 8 to 12 minutes of incremental exercise. The same protocol will be used for the 3-month posttest unless the initial workload has become too low to allow proper FES rowing technique. In this case, the initial workload will be the second workload from the pretest. To ensure attainment of peak exercise capacity, at least 3 of the following criteria must be met: 85% of age predicted maximal heart rate ($220 - \text{age}$), respiratory exchange ratio >1.1 at end exercise, plateau in oxygen consumption despite increasing workload, blood lactate level (Lactate Plus, Nova Biomedical, Waltham MA) of 8 mM or above, rating of perceived exertion of at least 17 on the Borg scale of 6 to 20, and precipitous decline in power $>20\text{W}$ during maximal leg stimulation. Peak oxygen consumption will be defined as the highest value achieved over 30 seconds.

Immediately after FES-rowing has stopped at the end of the VO₂max test, subjects will have a finger tip pricked with a safety lancet in order to get a drop of blood that will be used to measure peak lactate levels in whole blood. Peak lactate levels will be used to evaluate exercise intensity as well as to monitor training status.

Cardiac Output Row Testing

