Individuals will refrain from eating for 2 hours prior, from caffeine and alcohol for 24 hours prior, and from vigorous physical activity for 48 hours prior to testing. Cardiac output will be measured at rest and during a three to six minute FES-row steady state exercise bout at an intensity of 80% of peak heart rate. Cardiac Output is measured using the inert gas re-breathing method (Innocor, Innovision, Odense, Denmark), a previously validated non-invasive method for rest and exercise measures. Notably, inert gas re-breathing measurements of cardiac output do not require steady state conditions and hence can be

obtained during graded tests. An oxygen-enriched mixture of an inert soluble gas (0.5% nitrous oxide) and an inert insoluble gas (0.1% sulphur-hexafluoride) are used to indirectly assess pulmonary blood flow and lung volume, respectively. In the absence of pulmonary shunt, cardiac output = pulmonary blood flow. Arteriovenous oxygen difference will be derived by applying the Fick principle: arteriovenous oxygen difference = oxygen consumption / cardiac output. Subjects will do 2 re-breathing maneuvers at rest and 2 re-breathing maneuvers once they have achieved target heart rate.

Pulmonary Function Tests

Spirometry will be used to measure lung function, specifically the measurement of the amount (volume) and/or speed (flow) of air that can be inhaled and exhaled. Specifically, Forced Volume Vital Capacity (FVC) and Maximum Voluntary Ventilation (MVV) tests will be administered.

Regional Cerebral Blood Flow

A Near-Infrared Spectroscopy (NIRS; PortaLite, Artinis Medical Systems) probe placed on the forehead contralateral to the dominant hand will be used to measure blood oxygenation during maximal exercise testing. NIRS-derived blood oxygenation levels will be used as a measure of cerebral blood flow at the prefrontal cortex.

VI. BIOSTATISTICAL ANALYSIS

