This pilot project will employ a simple and straightforward statistical approach to compare changes within and between groups. Statistical significance will be set at 0.05, and power at 80%. Normality and equality of variance will be assessed using tests of skewness and kurtosis. Within and between group (FESRT+NIV vs. FESRT+shamNIV) comparison of changes will be made using a general linear model accounting for potential baseline differences and the intervention effect. Correlations between ventilation, aerobic capacity, and hemodynamics variables (cardiac output and arteriovenous oxygen difference) will be assessed by Pearson's or Spearman's coefficient depending on the normality of the variables. If significant relations are found, appropriate regression analyses will be employed.

VII. RISKS AND DISCOMFORTS

Moderate risks are associated with exercise testing and exercise training. Some discomfort and feeling of fatigue will be experienced during these tests. There are other risks associated with these tests including abnormal blood pressure responses, fainting, irregular, fast or slow heart rhythm, and in rare instances, heart attack, stroke, or death. Wearing the face-mask during the VO₂max testing and FES-row training may cause feelings of claustrophobia. Exercise training may induce some muscle or joint discomfort when beginning an exercise program and could result in tendonitis and/or musculoskeletal overuse injuries over time. Subjects may feel lightheaded or short of breath during use of the NIV machine and during the cardiac output measurement. The electrical stimulation unit can cause tingling, pins and needles sensations on the skin, skin irritation, increased muscle spasticity and autonomic dysreflexia (signs include: headache, nausea, rise in blood pressure, sweating, and goosebumps). There is some discomfort with the lancet used on the finger for lactate measurement and there is a small possibility of swelling and bruising at the site(s), there is also a slight chance that individuals become dizzy and even faint. Subjects may feel lightheaded or short of breath during the pulmonary function tests, there is also a slight chance that individuals become dizzy and even faint.

VIII. POTENTIAL BENEFITS

Volunteers will have the opportunity to participate in a supervised exercise program, which may

improve their overall cardiovascular fitness and endurance during activities of daily living as well as decrease risk of chronic disease.

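### Section VI tests aerobic capacity against an a-v O2 difference that is itself built from VO2, without fixing which test supplies that VO2 or barring shared-measurement tests; slopes are fitted only after significance

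*Combined protocol and SAP*

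**What the plan says.** Section VI (Biostatistical Analysis) states that "Correlations between ventilation, aerobic capacity, and hemodynamics variables (cardiac output and arteriovenous oxygen difference) will be assessed by" Pearson's or Spearman's coefficient, with significance at 0.05. Regression follows only where a correlation is significant. Section III hypothesises that gains in aerobic capacity will relate to gains in both CO and a-v O2 difference. Aim 2 (Section II) concerns "maximal cardiac output and arterio-venous oxygen difference after 3 months of FESRT+NIV".

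Section V supplies the measurements:

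- Under FES-Row-VO₂max Testing, aerobic capacity is the highest 30-second VO2 in a graded test, from "open circuit spirometry and expired gas analysis".
- Under Cardiac Output Row Testing, CO is taken at rest and in a "FES-row steady state exercise bout at an intensity of 80% of peak heart rate". The re-breathing schedule is: "Subjects will do 2 re-breathing maneuvers at rest and 2 re-breathing maneuvers once they have achieved target heart rate".
- The same subsection gives the ratio as "arteriovenous oxygen difference = oxygen consumption / cardiac output" and does not name the test that supplies the numerator. It also says that "inert gas re-breathing measurements of cardiac output do not require steady state conditions and hence can be" taken during graded tests.
- Study Assessments lists the VO2max and CO tests separately and adds: "Both NIV Support and Sham-NIV groups will perform tests with and without use of the NIV-machine".

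No section says which test or NIV condition feeds the correlations, or mentions the shared term.

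**The concern.** If the same VO2 reading is used as aerobic capacity and as the numerator of a-v O2 difference, its error enters both variables with the same sign. Zero correlation is then not the value expected when nothing real is happening, and p < 0.05 is not evidence that oxygen extraction contributed to the gain. The same applies to ventilation when it comes from the test that supplies the ratio's VO2, because open-circuit VO2 is computed from ventilation. It also applies, with the opposite sign, to CO against a-v O2 difference.

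The a-v O2 half of the Section III hypothesis is at stake. A false mechanism could be carried into the larger study that this pilot is meant to prepare. The significance gate before regression adds a second, separate bias: slopes that are reported only when significant are too large on average.

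**Working it through.** **The plan's own figures.** Section VI gives alpha 0.05 and 80% power but no expected correlation or SD, so the power cannot be reproduced. Aim 2 concerns the NIV arm. Thirty randomised and an assumed 1:1 split give n=15. The two-sided critical |r| is 0.514 at n=15 and 0.361 at n=30; 80% power at n=15 needs a true r of about 0.67.

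**Assumed inputs (the documents give none).** Within-person CV of VO2 v = 4-7% and of CO q = 7-10%. Analysis is of log changes (post minus pre). Averaging two re-breathings replaces q by q/√2.

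**Same-test VO2, no true change, independent errors.** Since dlog a-vO2 = dlog VO2 − dlog CO, the correlation of dlog VO2 with dlog a-vO2 is

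r = v / √(v² + q²).

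For example, v=4 and q=10 give 4/√116 = 0.37; v=7 and q=7 give 7/√98 = 0.71. Share of simulated trials significant at n=15 (40,000 per setting):

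| v, q (%) | r, one CO reading | significant | r, two averaged | significant |
|---|---|---|---|---|
| 4, 10 | 0.37 | 28% | 0.49 | 48% |
| 5, 10 | 0.45 | 40% | 0.58 | 66% |
| 4, 7 | 0.50 | 49% | 0.63 | 76% |
| 7, 10 | 0.57 | 65% | 0.70 | 88% |
| 7, 7 | 0.71 | 89% | 0.82 | 98% |

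Averaging makes matters worse, because VO2 error then dominates the ratio. Spearman gives 24-81% (41-96% averaged), and raw changes give 29-86% (47-97%). Pooling both arms (n=30) gives 54-99.6% (81-100%).

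**Same test, VO2 and CO changes correlated c.** Now r = (v − cq) / √(v² + q² − 2cvq). With v=5, q=10 and c=0.5 the numerator is 5 − 5 = 0. Over c = 0.3-0.5, about 5-69% of trials are significant (6-95% averaged).

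**Same test, VO2 truly rising wholly through CO.** With true-change SD s, r = 2v² / √[(s² + 2v²)(2v² + 2q²)]. For v=4, q=10, s=8: 32/√(96 × 232) = 0.21. Significant: 12-60% (18-77% averaged) at s = 8%, and 7-31% (9-41%) at s = 15%. True a-v O2 difference is unchanged in every one of these trials.

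**Separate tests, as scheduled.** If peak VO2 comes from the graded test and the ratio's VO2 from the CO bout, the errors are independent and about 5% are significant.

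**Other pairs.** Same-test ventilation against a-v O2 difference (ventilation CV 3-6%, extraction CV 3-5%): 16-74% (22-91% averaged). This falls to 7-25% (9-36%) if half the ventilation variance is offset by extraction, and to 5% if ventilation comes from another test. CO against a-v O2 difference, if tested at all: 89% to over 99% (65% to over 99%). Ventilation or VO2 against CO: about 5%.

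**Significance gate.** A true standardised slope of 0.3 is significant in about 19% of trials at n=15. The mean slope among those is about 0.63, roughly twice the truth. At n=30 it is about 0.47.

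**The case against.** The strongest reply is that the schedule does not contain the damaging case. VO2max and CO tests are listed separately, re-breathing is scheduled only at rest and at target heart rate, and the Fick formula stands in the CO subsection. The remark about graded tests describes the method rather than a visit procedure. This largely stands: using the bout's own VO2 is the natural reading, and it gives about 5%. A reader might infer that the plan as scheduled will manufacture an a-v O2 relation; the documents do not support that. Still, they do not commit to the natural reading. Aim 2 asks for maximal CO, which a bout at 80% of peak heart rate cannot supply, and an analyst meeting that wording could take CO in the graded test or divide peak VO2 by a submaximal CO.

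A second tempting inference is that separate-test correlations are also mostly false. Significance does rise to 10-63% (14-80% averaged) if the two tests' VO2 changes correlate 0.5-0.8. With independent errors, however, such a correlation requires real shared change. If VO2 in the bout truly changed while CO did not, a-v O2 difference truly changed. These are not false-positive rates, and there is no reason to forbid the separate-test analysis.

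Third, effort and workload may move VO2 and CO together within a test. That is right, and at the low end it removes the excess; at the high end most of it remains. Fourth, testing CO against a-v O2 difference is only one reading of Section VI, and no aim asks for it. That is why it is not the main point.

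**Conclusion.** The concern holds in a conditional form. Section VI permits a zero-correlation test between a-v O2 difference and a quantity from which it was computed, and nothing in the documents rules that out. On the scheduled design with the bout's VO2 in the ratio, the error-driven false-positive rate is about 5%. If one test's VO2 enters both variables, it is 28-89% at n=15 (48-98% with two CO readings averaged) under independent errors, about 5-69% (6-95%) if VO2 and CO changes correlate 0.3-0.5, and 7-60% (9-77%) if VO2 truly rises only through CO. All CVs and the 15-per-arm split are assumptions. The inflation of gated slopes does not depend on the VO2 source.

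A reader might extend this to the trial's main comparison. It does not reach it: Aim 1 compares aerobic capacity between arms and uses no ratio. The affected analysis is secondary and mechanistic, in a pilot. It should be fixed because the remedy costs almost nothing.

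**What to change.** In Section VI:

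1. Take peak VO2 and ventilation from the graded test, and the VO2 in the a-v O2 ratio from the test that measures CO. State one NIV condition, the same at both visits, and whether the two re-breathings are averaged. Reconcile Aim 2's maximal CO with the bout at 80% of peak heart rate, or label the Aim 2 result submaximal.
2. Do not test a-v O2 difference for zero correlation with CO, VO2 or ventilation from the same measurement. Report instead the mean of each term in dlog VO2 = dlog CO + dlog a-vO2, with 95% CIs, all from one test. Correlations of peak VO2 gain or ventilation gain with a-v O2 gain may still be tested when the two sides come from separate tests.
3. Report the slope and 95% CI for every planned relation whatever its p-value, and delete the condition that regression follows only a significant correlation.

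Cost: analysis wording and a few lines of code; no new data or visits. The decomposition describes average contributions, so it complements the between-person relations in Aim 2 and does not replace them. There will be fewer p-values, and intervals will be wide at n=15: an observed r of 0.5 has 95% CI −0.02 to 0.81, and a mean log change with SD 0.10 has half-width 2.145 × 0.10/√15 = 0.055. Error in CO also shrinks slopes on CO, to s²/(s² + q²) with two readings averaged: 0.39 (s=8, q=10) to 0.82 (s=15, q=7). That weakens a relation but does not create one.

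### Aim 2 regressions are fitted only after a significant correlation, so with about 15 NIV participants the reported slopes are selected and, unless the true correlation is strong, exaggerated on average

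*Combined protocol and SAP*

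**What the plan says.** Section II, Aim 2, sets out to relate gains in ventilation to gains in the determinants of aerobic capacity: "maximal cardiac output and arterio-venous oxygen difference after 3 months of FESRT+NIV in high level spinal cord injury". Section III (Subject Selection) gives the sample: "Thirty individuals with high level SCI" are randomized to training "with either NIV or sham NIV". No allocation ratio is stated.

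Section VI handles Aim 2 in two steps. The first has no condition attached: "Correlations between ventilation, aerobic capacity, and hemodynamics variables (cardiac output and arteriovenous oxygen difference) will be assessed by Pearson's or Spearman's coefficient", the choice depending on normality. The second does: "If significant relations are found, appropriate regression analyses will be employed". The threshold comes from the same section: "Statistical significance will be set at 0.05, and power at 80" per cent. Section VI does not give the regression model, the arm or arms used, whether changes or levels are related, any confidence interval, or how non-significant relations will be reported.

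**The concern.** Aim 2 asks how strongly gains in ventilation go with gains in cardiac output and arteriovenous oxygen difference. The slope answers that in physical units. If it is estimated only when the correlation is significant, the slopes that appear are those that chance has tended to push upward, and the rest are never estimated.

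In a small sample the cut-off is high, so a weak or moderate relation can pass only by looking stronger than it is. A reader would then see too steep a mechanistic relation. A relation that fails the test would have no slope at all, and that absence could be mistaken for evidence of no relation. This is a separate matter from any correlation built in by deriving one variable from another.

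**Working it through.** The documents state no expected correlation, slope or sample-size derivation for Aim 2, so there is no figure of the plan's to reproduce.

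**Inputs.** Alpha is 0.05 (section VI), taken as two-sided because sidedness is not stated. Thirty people are randomized to two arms (section III). Assuming 1:1, the NIV arm has 30/2 = 15. Aim 2's wording ("after 3 months of FESRT+NIV in high level spinal cord injury") supports using that arm alone. The true correlation ρ is unknown, so a range is shown.

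**Step 1: cut-off.** The critical value is |r| = t/√(n − 2 + t²).
- n=15: t = 2.160 on 13 df, so 2.160/√(13 + 4.67) = 0.514.
- n=12 (some loss): 0.576.
- n=30 (arms pooled): 0.361.

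**Step 2: what 80% power would need.** By the Fisher z approximation, ρ = tanh((1.960 + 0.842)/√(n − 3)). At n=15 this is tanh(2.802/3.464) = 0.67. At n=30 it is 0.49.

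**Step 3: slope given significance.** Pairs were simulated from a bivariate normal distribution with unit variances, so that the true slope equals ρ. The Pearson test was applied, with 200,000 replicates per ρ, and the least-squares slope was averaged over the significant replicates.

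| ρ | Pass, n=15 | Mean reported ÷ true slope, n=15 | Reported slopes above truth, n=15 | Pass, n=30 | Mean reported ÷ true slope, n=30 |
|---|---|---|---|---|---|
| 0.2 | 11% | 2.88 | 96% | 19% | 2.23 |
| 0.3 | 19% | 2.09 | 99% | 37% | 1.58 |
| 0.4 | 33% | 1.62 | 95% | 61% | 1.26 |
| 0.5 | 50% | 1.34 | 83% | 83% | 1.09 |
| 0.6 | 70% | 1.16 | 68% | 96% | 1.02 |
| 0.7 | 88% | 1.06 | 56% | over 99% | 1.00 |
| 0.8 | 98% | 1.01 | 51% | over 99% | 1.00 |

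At n=12 the ratios are 2.27, 1.45 and 1.11 at ρ = 0.3, 0.5 and 0.7.

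**Step 4: the condition is the cause.** Fitted regardless of significance, the least-squares slope is unbiased under the linear model. At n=15 and ρ = 0.3, 19.3% of samples pass, with a mean slope of 0.626. The other 80.7% must therefore average (0.3 − 0.193 × 0.626)/0.807 = 0.22. The rule shows the high group and leaves out the low one.

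**Step 5: a relation that fails.** An observed r of 0.3 at n=15 is below 0.514. Its Fisher 95% interval is tanh(0.310 ± 1.96/√12), or about −0.25 to 0.70, so it is compatible with anything from a weak negative to a strong positive relation.

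**The case against.** The best reply is that this is a self-described pilot, that Aim 2 is exploratory, and that following a correlation screen with regression is common practice on which no efficacy conclusion depends. That limits the importance of the point. It does not remove the bias, which comes from a rule the plan states rather than from a silence.

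A second reply is that strong correlations are possible, since section V derives one variable from two others ("arteriovenous oxygen difference = oxygen consumption / cardiac output"), and for strong relations the bias is negligible. This stands for pairs that share terms in that formula. Ventilation is not a term in it, and the documents give no expected correlation, so a strong one cannot be presumed for the ventilation relations.

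Three stronger readings are tempting, and the documents do not support them:

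- *Each reported slope is too large.* Each is selected, but the excess is an average over repeated trials. At n=15 about 17% of reported slopes are at or below the truth at ρ = 0.5, and about half are at ρ = 0.8.
- *Non-significant relations get no estimate.* The coefficients are computed without condition, and a coefficient is an estimate. For a Pearson r, a reader could form an interval from r and n if r is reported. What is missing is the slope, together with any commitment to report intervals.
- *The inflated slopes will be used to size the next trial.* Section III says only that the project prepares for a larger study of the impact of FESRT+NIV. It does not say that the Aim 2 slopes will be used in planning it.

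**Conclusion.** The point holds as a limited one. Every Aim 2 slope reported under section VI is conditional on significance and, unless the true correlation is about 0.7 or more, exaggerated on average. With 15 NIV participants the excess runs from 2.1 times at a true correlation of 0.3 to 1.16 times at 0.6, and falls to 6% at 0.7 and 1% at 0.8.

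This rests on 1:1 allocation, analysis of the NIV arm alone, a two-sided test, bivariate normality and Pearson's coefficient. The Spearman option was not simulated. With the arms pooled the problem is smaller but still material for weak relations. The pooled figures treat all 30 as one population and so leave out any distortion from a difference between arms.

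The Aim 1 comparison is not affected. It uses a general linear model that does not depend on this step.

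**What to change.** Replace the last sentence of section VI with:

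> For each Aim 2 relation between the change in ventilation and the change in aerobic capacity, cardiac output or arteriovenous oxygen difference, the correlation and a linear regression slope will be reported with 95% confidence intervals in NIV-arm participants with paired measurements, regardless of statistical significance; any analysis pooling both arms will include a term for arm.

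The arm term matters because a treatment effect on both variables could by itself produce a slope in pooled data. Aerobic capacity is included because section VI lists it among the variables to be correlated.

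No extra data, visits or participants are needed. The cost is slightly more reporting, and weak relations will be shown with wide intervals.
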